5.2 Contraception Recommendations

Contraception Requirements for Females:

Postmenopausal is defined as:

- Age > 55 years with no menses for 12 or more months without an alternative medical cause.

If female, subject must be either post-menopausal, permanently surgically sterile (bilateral oophorectomy, bilateral salpingectomy or hysterectomy) or a woman of childbearing potential (WOCBP) and must practice at least one of the following methods of birth control, throughout the study including 30 days after the last study drug dose is given.

- Contraceptives and/or hormonal replacement therapies containing only progestins (such as those containing norethindrone, desogestrel, or levonorgestrel) or those containing progestins

with non-ethinyl estradiol estrogens (e.g., esterified or conjugated) associated with inhibition of ovulation initiated at least 1 month prior to study Baseline Day 1.

- Bilateral tubal occlusion/ligation.
- Intrauterine device (IUD).
- Intrauterine hormone-releasing system (IUS).
- Vasectomized sexual partner(s) (the vasectomized partner(s) provided the vasectomized partner has received medical assessment of the surgical success and is the sole sexual partner of the trial participant).
- Male or female condom with or without spermicide.
- Cap, diaphragm or sponge with spermicide.
- A combination of male condom with either cap, diaphragm or sponge with spermicide (double barrier method).
- True abstinence: Refraining from heterosexual intercourse when this is in line with the preferred and usual lifestyle of the subject, (periodic abstinence [e.g., calendar, ovulation, symptothermal, post-ovulation methods] and withdrawal are not acceptable).

For male study subjects no contraception is required.

5.3 Prohibited Medications and Therapy

Subjects must not be taking any prohibited medications or supplements listed in Section 5.1 for at least 14 days prior to the first dose of any study drug and not use these during the entire treatment period and for 14 days following discontinuation of study drug.

Contraceptives and/or hormonal replacement therapies containing only progestins (such as those containing norethindrone, desogestrel, or levonorgestrel) or those containing progestin with non-ethinyl estradiol estrogens (e.g., esterified or conjugated) may be used with GLE/PIB at the discretion of the Investigator.

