4.2 Study Procedures

4.2.1 Hepatitis C Diagnosis and Recruitment Screen

Prior to study roll out, site investigators will meet with drug treatment center leadership to outline procedures for offering study participation to drug center clients. The OTP will facilitate HCV antibody testing and/or HCV RNA testing through rapid testing or phlebotomy. Prior to study enrollment, participants will complete an initial screening questionnaire, which will explore if the participant has previously been diagnosed with HCV, and if previously diagnosed, previously treated for HCV with oral direct-acting antiviral (DAA) therapy. Individuals who report previous HCV treatment with oral DAA therapy will not be eligible for study enrollment. Potential participants will also be asked about their current medications to ensure they are not currently taking any medication prohibited by the study (see Sections 5.1 and 5.3). Individuals who report taking a study-prohibited medication will not be eligible for study enrollment. These screening questions will be mixed with other questions to ensure that participants remain unaware of study eligibility criteria. Individuals who are HCV antibody or HCV RNA positive on testing and remain study eligible after completing the screening questionnaire will be offered enrollment into the study and if willing, go through the process of informed consent.

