4.2.9 Study Arms

Intervention – Test and Treat strategy: This will consist of a meeting (in person, by phone or over video) with a trained peer mentor who will meet with the study participant after randomization to communicate information about HCV in a manner that takes into account an understanding of experiences with HCV and care access faced by people who use drugs, the potential harms of untreated HCV and the benefits of HCV treatment.

Peer Training, Monitoring, and Quality Assurance. Peers will receive training modelled on our previous experience training peers for HCV treatment support. The training will be provided as modules. Topics to be addressed in the modules are: 1) Power of peer mentoring and key values including confidentiality and respect for all persons; 2) Tools for effective communication; 3) HCV disease and substance use disorder including importance of adherence to medications/visits; 4) Self-care in the peer-mentor role; 5) review of patient tracking tools. Peers will also have an individual training session. Individual sessions will prepare the peer for their peer support role including building communication skills to enhance conversations to support HCV care engagement. Peers will be trained to improve their communication skills with a focus on: 1) providing accurate information; 2) working with patients on goal setting for HCV treatment adherence; and 3) identifying barriers to retention in care. We will ensure peers have demonstrated competency in all of their tasks through knowledge and performance assessments as judged through role-plays.

Peer support and care coordination tasks. Peers will be responsible for maintaining contact with patients in the test and treat arm. They will also complete adherence and food use with medication surveys at weekly contacts. He or she will also communicate the need to return for results of follow up testing and follow through with recommended treatment. The Peer will also communicate to the patient the expected timing of follow up appointments at the drug treatment center and will offer support for the duration of HCV treatment. Up to 15 peers will be enrolled in this study.

The treatment initiation visit at the drug treatment center will depend on the standard amount of time it takes to get results of laboratory testing back to the drug treatment center site. We expect this to be 3-5 days.

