The peer will contact the patient 2 days before and the day before the scheduled appointment to remind that participant about the appointment.

Peers will have a standard protocol for at least weekly phone contact with participants through post-treatment week 12, and will be available to answer participant questions as needed. Peers will maintain a log of peer contact, which will be submitted to research program staff weekly.

Peers will have access to drug treatment clinic staff for support with trouble shooting any arising matters.

Peers will submit weekly logs of participant contact to the research program coordinator and meet as a group (both peers and research program coordinator at each site, either virtually or in person) to review best practices and address any issues or questions related to effective performance as a peer.

If the participant does not want to work with the assigned peer, they can choose not to receive peer services.

HCV treatment initiation. At the treatment initiation visit, if still eligible for the study after all Day 0 results are available (detectable HCV RNA, platelet count >150,000, not pregnant) the patient will be offered immediate initiation of HCV treatment.

HCV treatment will be initiated at the drug treatment center. Participants will be provided a 4-week supply of glecaprevir/pibrentasvir (GLE/PIB) combination. For patients who report living and other situations that pose barriers to safe storage of a 4-week supply of medications, individual drug treatment centers will develop processes for providing GLE/PIB in quantities that can be safely stored by the participant.

At the treatment initiation visit, participants will be given a follow up appointment for 8 weeks after treatment initiation (expected end of treatment) with designated drug treatment center staff.

Standard of Care Referral to Offsite Location: Participants randomized to standard of care arm will be referred to an offsite HCV treatment site.

Using a signed release of medical information form, research staff will follow up with the referral site to see if the patient scheduled and subsequently attended an appointment and collect information on subsequent progress along the HCV care continuum.

If the patient is confirmed to have scheduled the appointment, study staff will contact the evaluating physician to make them aware that the study may provide GLE/PIB for HCV treatment.

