5 STUDY ACTIVITIES

5.1 Inclusion and exclusion Criteria

Inclusion criteria: Participants must meet all of the following inclusion criteria to be eligible for participation

- ✓ Ability and willingness of participant to provide written informed consent
- ✓ Men and women age ≥ 18 to ≤ 70 years at study entry
- ✓ HCV antibody positive/Detectable HCV RNA
- ✓ HCV treatment naïve (no prior treatment with an approved or investigational oral DAA therapy)
- ✓ Negative pregnancy test at screening or at the day of treatment initiation (females of childbearing potential only)
- ✓ If co-infection with Human Immunodeficiency Virus (HIV) is documented, the subject must be anti-retroviral treatment (ART) naïve with CD4 T cell count >500 cells/mm³ OR on a stable ART regimen (containing only permissible ART – Raltegravir; dolutegravir; Rilpivirine; Elvitegravir/cobicistat; Tenofovir disoproxil fumarate; Tenofovir alafenamide; Emtricitabine; Lamivudine and/or Abacavir, bicitegravir)

Exclusion criteria: Subjects who meet any of the following exclusion criteria are not to be enrolled in this study

- ✓ Women who are pregnant or breastfeeding, or considering becoming pregnant during the study and for 30 days after the last dose of study drug
- ✓ Known allergy/sensitivity or any hypersensitivity to components of study drugs or their formulation
- ✓ Current or history of decompensated liver disease (including but not limited to encephalopathy, variceal bleeding, or ascites) prior to study entry

- ✓ History of hepatocellular carcinoma (HCC)
- ✓ Any history of active Hepatitis B or positive HBsAg test
- ✓ Platelet count < 150,000/mm³
- ✓ HCV RNA undetectable
- ✓ History of clinically significant abnormalities or co-morbidities that make the subject an unsuitable candidate for this study, in the opinion of the investigator.
- ✓ Women of childbearing potential that are not practicing at least one specified method of birth control (refer to Section 5.2) that is effective from Study Day 1 through at least 30 days after the last dose of study drug.
- ✓ Subject is currently taking any of the following prohibited medications:
 - Red yeast rice (monacolin K), St. John's Wort
 - Carbamazepine, Dabigatran, efavirenz, phenytoin, pentobarbital, phenobarbital, primidone, rifabutin, rifampin
- ✓ Subject is not able or willing to safely discontinue the prohibited medications or supplements listed below at least 14 days prior to the first dose of GLE/PIB:

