5.4 Prior and Concomitant Therapy

The investigator should confirm that a concomitant medication/supplement can be safely administered with study drug. Some medications may require dose adjustments due to the potential for drug-drug interactions (DDIs).

Any medication/supplement or vaccine (including over-the-counter or prescription medicines, vitamins and/or supplements) that the subject is receiving from the time of signing the consent through the Treatment Period must be recorded in the electronic case report form (eCRF) along with the reason for use, date(s) of administration including start and end dates, and dosage information including dose, route and frequency. The investigator should review all concomitant medications for any potential DDIs.

Any questions regarding concomitant or prior therapy should be raised to the Sponsor Medical Contact.

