APPENDIX A. SCHEDULE OF EVENTS (ALL PARTICIPANTS)

	Recruitment Screen	Day 0	Treatment Day 1	Treatment Week 4	End of Treatment -0d/+30d	Post-Treatment Week 12 -14d/+30d	Post-Treatment Week 24 -14d/+30d	Post-Treatment Week 36 -14d/+30d	Early D/C Visit
Eligibility Review ^a	X	X							
Vital Signs ^b		X							
Demographics		X							
Medical History		X							
Concomitant Medications ^c		X			X				
Randomization		X							
Referral to HCV Treatment (SOC Arm Only)		X							
AE/SAE Collection ^d			→	→	→				
Laboratory Testing									
HBsAg		X							
Pregnancy Test ^e		X							
CBC ^f		X							
HCV RNA ^g		X			X	X		X	X
CMP		X			X	X			X
Urine Toxicology Screen		X			X	X	X	X	
Dried Blood Spot		X			X	X	X	X	X
Surveys/Questionnaires									
Study Survey		X			X	X	X	X	
PRO/QOL Measures		X			X	X	X	X	
Intervention Arm Only									
Peer Contact ^h		X	→	→	→	→			X
Study Drug Dispensation ⁱ			X	X					

^aIncluding documentation of HCV infection (antibody) and treatment history.

^bIncluding height, weight, temperature, pulse, respiratory rate, and blood pressure.

^cAll medication (including supplements and over-the-counter) will be collected.

^dAE/SAE collection starts with initiation of DAAs, continues through 30 days after last DAA dose.

^eFor all participants of childbearing potential. Urine or serum test.

^fWith or without differential.

^gCLIA certified.

^hPeer contact to occur weekly and as needed between visits until SVR 12. Contact can be in-person, via phone, or video.

ⁱStudy drug can be dispensed in smaller amounts more frequently if participant is unable to maintain 4-week supply at home.

APPENDIX B. SCHEDULE OF EVENTS (PARTICIPANTS WHO DO NOT START HCV TREATMENT BY WEEK 12 AFTER RANDOMIZATION IN EITHER ARM)

For participants who have not initiated treatment by Week 12 after randomization, complete the following.

	Week 12 after randomization -14d/+30d	Week 24 after randomization -14d/+30d	Week 36 after randomization -14d/+30d	Week 56 after randomization -14d/+30d
Laboratory Testing				
Urine Toxicology Screen	X	X	X	X
Dried Blood Spot	X	X	X	X
HCV RNA ^e		X		X
Surveys/Questionnaires				
Study Survey	X	X	X	X
PRO/QOL Measures	X	X	X	X
Rescreen for SOC Participants to Rollover to Intervention Arm				
Eligibility Review		X		
Vital Signs ^a		X		
Concomitant Medications ^b		X		
HBsAg		X		
Pregnancy Test ^c		X		
CBC ^d		X		
CMP		X		
Peer Contact ^f		→		

^aIncluding height, weight, temperature, pulse, respiratory rate, and blood pressure.

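### Sections 4.2.1, 5.1 and 5.3 are inconsistent on prohibited medications, and neither the initiation-visit check nor the dispensing visits in Appendix A name a medication review

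*Combined protocol and SAP*

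**What the plan says.** **Screening (4.2.1).** Before consent, a questionnaire asks about current medications, pointing to 5.1 and 5.3 for the list. The consequence is unqualified: "Individuals who report taking a study-prohibited medication will not be eligible for study enrollment".

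**Eligibility (5.1).** The list is in two groups.
- Group 1 (red yeast rice, St. John's Wort, carbamazepine, phenytoin, rifampin and others): excluded if currently taken. No interval since stopping is given.
- Group 2 (atorvastatin, lovastatin, simvastatin, astemizole, cisapride, terfenadine, ethinyl estradiol): excluded only if the subject is "not able or willing to safely discontinue the prohibited medications or supplements listed below at least 14 days prior to the first dose". Statin users may switch or interrupt, and their interval is the longer of 14 days and 10 half-lives.

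**Prohibited medications (5.3).** One rule for both groups: "Subjects must not be taking any prohibited medications or supplements listed in Section 5.1 for at least 14 days prior to the first dose". The bar continues through treatment and for 14 days afterwards.

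**Treatment initiation (4.2.9).** The visit is timed by laboratory turnaround: "We expect this to be 3-5 days". If the participant is still eligible once Day 0 results are in, with RNA, platelets and pregnancy given in brackets, "the patient will be offered immediate initiation of HCV treatment".

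**During treatment.** Under 5.4, any medication "that the subject is receiving from the time of signing the consent through the Treatment Period must be recorded", with dates, and the investigator is to review all of them for interactions. Section 5.5 lists introduction of a prohibited medication as a reason for withdrawal where continuing study drug would put the subject at risk. In Appendix A the row "Concomitant Medications ^c" is marked at Day 0 and End of Treatment. Study drug is dispensed at Treatment Day 1 and Week 4.

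**The concern.** The order of events makes the first inconsistency matter in practice. The 4.2.1 questionnaire comes before the offer of enrolment, so a site that follows it never reaches 5.1's question of whether a statin user could stop or switch. A site that works from 5.1 enrols the same person. Eligibility can therefore differ between the five sites for reasons nobody chose.

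The second issue is safety. The protocol sets its own 14-day interval before first dose, but the visit at which first dose is given names no item that would confirm it. During dosing, the protocol bars these drugs, requires them to be recorded and lists their introduction as a withdrawal reason, yet the schedule that sites work from marks no medication review when drug is handed out.

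**Working it through.** **1. The sections side by side**

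| Person at screening | 4.2.1 | 5.1 | 5.3 | Can all be obeyed? |
|---|---|---|---|---|
| On a listed statin, able and willing to stop or switch | Not eligible | Eligible; longer of 14 days and 10 half-lives | At least 14 days off | No: 4.2.1 and 5.1 disagree on eligibility |
| On astemizole, cisapride, terfenadine or ethinyl estradiol, able and willing to stop | Not eligible | Eligible; at least 14 days | At least 14 days off | No: same disagreement |
| On a Group 1 drug now | Not eligible | Not eligible | May not be dosed | Yes |
| Stopped a Group 1 drug a few days ago | Not caught, since it asks about current use | Not excluded; no interval | At least 14 days off | Yes, if first dose waits |

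Ethinyl estradiol needs a qualification. A user of childbearing potential must also have a contraceptive method listed in 5.2, and ethinyl-estradiol products are not on that list. The statin row is the cleanest example.

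**2. Statin interval.** The intervals in 5.1 and 5.3 differ only when 10 half-lives exceed 14 days, that is, for a half-life above 14 / 10 = 1.4 days. The documents give no half-lives, so they do not show whether this ever changes a date.

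**3. Washout against the initiation visit.** Assume the 3-5 days run from Day 0. Let d be the days between stopping the drug and Day 0, and v the days from Day 0 to the visit.

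Shortfall = 14 − d − v

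- Stopped on Day 0 (d = 0): 14 − 5 = 9 to 14 − 3 = 11 days short.
- d = 8: 14 − 8 − 5 = 1 to 14 − 8 − 3 = 3 days short.
- d = 11, v = 3: 14 − 11 − 3 = 0, so from d = 11 there is no shortfall.

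The interval therefore needs active checking for people who stopped less than about 9 to 11 days before Day 0.

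**4. Primary endpoint.** The window is 12 weeks = 84 days from randomization. A washout begun on Day 0 leaves 84 − 14 = 70 days.

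**5. Schedule.** Study drug is dispensed at two scheduled visits, Treatment Day 1 and Week 4. Concomitant Medications is marked at 0 of the 2.

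**6. Number affected.** The documents give no prevalence of use. Each 1% of the 124 participants is 0.01 × 124 = 1.24 people.

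**The case against.** Much can be said for the plan. The condition in 4.2.9 is that the participant is still eligible. Its bracket reads as the results pending from Day 0, not a full eligibility list; it also omits HBsAg, which is an exclusion elsewhere. Nothing there waives 5.3. Eligibility is reviewed at the Recruitment Screen and Day 0. The 3-5 days is an expectation tied to laboratory turnaround, not a deadline, and a washout finished before Day 0 fits it. For recent stoppers, 5.1 governs enrolment and 5.3 governs dosing, so a site can satisfy both. Section 5.4 imposes a continuing duty to record and review.

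All of this stands, and it rules out three stronger readings that a reader might infer:

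- *The same patient could be excluded, washed out or dosed at once, depending on the section.* No listed drug gets all three outcomes. Sections 4.2.1, 5.1 and 5.3 each bar immediate dosing of a current user.
- *A drug started after Day 0 goes unasked until dosing is over.* The duty in 5.4 is continuous. What is missing is a scheduled prompt at the dispensing visits.
- *The comparison of arms is biased.* Medication screening precedes randomization, which is separate at each program, so site differences in screening fall on both arms. A washout could delay initiation in the test and treat arm, but 4.2.9 says the study may supply the same drug to referral participants, so a difference between arms is speculative.

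The objection does not reconcile 4.2.1 with 5.1 for Group 2 drugs, and it does not supply a named check of the interval or a medication mark at the dispensing visits.

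**Conclusion.** The concern holds as an internal inconsistency with a modest safety consequence. Sections 4.2.1 and 5.1 contradict each other on whether a willing Group 2 user is eligible. Sections 5.1 and 5.3 state different intervals for statins, and only 5.3 states one for Group 1; these can be met together but are easily misapplied. The 14-day interval has no named check at the initiation visit, and Appendix A does not match the obligations in 5.3 to 5.5.

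The 9-11 day shortfall applies to someone who stops a listed drug on Day 0 and is dosed at the expected time without a medication check. It rests on counting the 3-5 days from Day 0. The primary endpoint is little affected. Any effect on time to initiation depends on how many people need a washout, which the documents do not give. Which clinical rule should apply is for the sponsor.

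**What to change.** 1. Reconcile 4.2.1, 5.1 and 5.3 so that one rule, including its interval, applies to each listed drug. The sponsor decides which.
2. Have the still-eligible condition in 4.2.9 refer to that reconciled rule, so that it is confirmed before first dose.
3. Mark Concomitant Medications at Treatment Day 1 and Week 4 in Appendix A, in line with 5.3 to 5.5.

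The cost is a wording amendment and one medication question at two visits that already exist. Depending on the rule chosen, a few participants may start later or be screened out.

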5.4 Prior and Concomitant Therapy

The investigator should confirm that a concomitant medication/supplement can be safely administered with study drug. Some medications may require dose adjustments due to the potential for drug-drug interactions (DDIs).

Any medication/supplement or vaccine (including over-the-counter or prescription medicines, vitamins and/or supplements) that the subject is receiving from the time of signing the consent through the Treatment Period must be recorded in the electronic case report form (eCRF) along with the reason for use, date(s) of administration including start and end dates, and dosage information including dose, route and frequency. The investigator should review all concomitant medications for any potential DDIs.

Any questions regarding concomitant or prior therapy should be raised to the Sponsor Medical Contact.

5.5 Withdrawal of Subjects and Discontinuation of Study

A subject may voluntarily withdraw or be withdrawn from the study at any time for reasons including, but not limited to, the following:

- Clinically significant abnormal laboratory results or AEs, which rule out continuation of the study drug, as determined by the Investigator or the Sponsor Medical Director.
- The Investigator believes it is in the best interest of the subject.
- The subject requests withdrawal from the study.
- Eligibility criteria violation was noted after the subject started study drug, when continuation of the study drug would place the subject at risk.
- Introduction of prohibited medications or dosages when continuation of the study drug would place the subject at risk.
- The subject becomes pregnant while on study drug and the investigator, after discussion with the subject, concludes that the benefit of continuing therapy does NOT outweigh the risk.
- Subject is significantly non-compliant with study procedures, which would put the subject at risk for continued participation in the trial.
- For subjects to be considered lost to follow-up, reasonable attempts must be made to obtain information on the final status of the subject. At a minimum (unless otherwise required by local regulations), 2 phone calls must be made and 1 certified letter must be sent and documented in the subject's source documentation. If a patient is not reachable by phone a letter will be sent or visit conducted to the address on file to reestablish contact with the patient. The letter/visit will alert the patient of study team efforts to reach them as well as provide the viable contact methods the patient may use to contact the study team.

Sponsor may terminate this study prematurely, either in its entirety or at any site. The Investigator may also stop the study at his/her site if he/she has safety concerns. If the study terminates for safety reasons, the sponsor will promptly notify the Investigator.

Refer to Section 6.3 for additional discontinuation criteria relating to Toxicity Management.

